2.1 of 4 May 2012 including second amendment (d)	201116/SA2 201116/SA3 (re-submission)	25 May 12	6 Jun 12	10 Apr 12		8 Mar 13		7 Sept 2012 (Barcelona)			23 Jul 2012	10 Jul 2012.
3.0 of 30 Jan 2014 including third amendment (e)	201116/SA4	18 Mar 14	4 Apr 14	8 Apr 14			10 April 2014	4 April 2014				
4.0 of 1st Dec 2015 including 4th amendment (f)	201116/SA5	27 Jan 2016	1st Mar 2016	5 Jul 2016								
4.1 of 13 July 2016 including non substantial amendment (g)	Not applicable	Not applicable	Not applicable									
5.0 of 9th July 2018 including 5th amendment (h)	Not applicable	Not applicable	20 Aug 2018	2 Oct 2018								
5.1 of June 24th 2019 including non-substantial amendment (i)	Not applicable	Not applicable	Not applicable	Not applicable								

NCA: National Competent Authority, EC: Ethic Committee

- (a) Removal of pharmacogenetic study, trial site list update, clarifications requested by the NCRN, correction of typing errors, addition of formulae for calculation of creatinine clearance (Appendix 8)
- (b) Funding arrangement for cefixime and temodal, drug management in The Netherlands (Appendix 11)
- (C) Addition of Guidelines for administering temozolomide to patients in the United Kingdom who have difficulty swallowing temozolomide capsules (Appendix 12)
- (d) Additional instructions about vincristine dose adjustments, and in case of bone marrow disease; clarification of SAE reporting; update of the study calendar; correction of typing errors
- (e) information about hepatic toxicities occurring in patients treated with Temozolomide, revision of Temodal SmPC, revision of Helsinki declaration, update of staff contacts
- (f) Addition of 40 extra patients with recurrent RMS, and non substantial modifications (changes in staff list, protocol clarifications)
- (g) update of staff contact list (sponsor)
- (h) addition of contraindications following update of irinotecan's SmPC, and non substantial modifications (changes in staff list, clarifications of biostatistical considerations, update of temozolomide and vincristine's SmPC without impact on patient's safety)
- (g) removal of a withdrawal criterion; definition of the Last Visit of the Last Subject (LVLS) as the last VI/VIT administration + 6 months to have relevant data in terms of response after 2 cycles.
- (i) removal of a withdrawal criterion: "Local therapy after 2nd cycle of study treatment", in line with Steering Committee recommendations to perform analysis on local treatment received after VI/VIT, in order to explain the much larger effect of VIT compared to VI on overall survival than progression-free survival ; and clarification of the Last Visit of the Last Subject (LVLS), defined as the last VI/VIT administration followed by 6 months to have relevant data in terms of response after 2 cycles

4. SYNOPSIS

Will be attached to the protocol

5. INTRODUCTION AND STUDY RATIONALE

5.1. Study disease

Rhabdomyosarcoma (RMS) is a soft tissue sarcoma derived from muscle precursor cells. It is the commonest form of soft tissue sarcoma in children < 15yrs, accounting for around 4% of paediatric malignancies and with a peak incidence in young children < 5yrs. However, RMS can occur at all ages and overall 41% of cases occur in the adult population [Sultan 2009]. The pattern of disease changes with age, with alveolar and metastatic tumours commoner in older children/young people and pleomorphic RMS and not otherwise specified histologies commoner in adults. Adults are more likely to present with disease at unfavourable sites. The likely outcome in RMS depends on a number of risk factors at presentation including age, site, tumour size, histo-logy and presence of nodal or metastatic disease and initial treatment is now tailored according to risk.

Around 85% of children with RMS have localised disease at presentation. Within the SIOP experience the 3 yr event free survival of patients achieving complete local control is 64% and 36% of patients who relapse can be salvaged [Chisholm 2011]. Among patients experiencing relapse, the most frequent site of relapse is locoregional (76%) with only 15% of patients having an isolated metastatic recurrence [Chisholm 2010]. Survival after relapse is affected by several factors, the most important being the type of recurrence, previous radiotherapy, time of relapse and the initial tumour size [Chisholm 2010]. Survival after an isolated local relapse is around 50% at 3 years whereas it is only 13-14% at 3 years after a metastatic relapse [Dantonello 2008, Mattke 2009, Mazzolini 2005, Pappo 1999, Pappo 2001, Pappo 2007, Chisholm et al 2010]. This finding means that we urgently need new chemotherapy agents and/or targeted agents for systemic treatment of RMS. Another key factor is the ability to deliver good local therapy to locally relapsing tumours; where patients have previously received radiotherapy, local therapy may be limited to aggressive surgery. Surgical clearance may be aided by effective new systemic therapies justifying the use of volumetric response of the target lesions to the chemotherapy as the main evaluation criteria in the current study.

Most patients with relapsed rhabdomyosarcoma have measurable disease at local and/or metastatic sites at relapse. In this study we will test the new combination of vincristine, irinotecan and TMZ in RMS, using objective volumetric response after 2 cycles of treatment as our primary endpoint.

5.2. Irinotecan

Irinotecan is a camptothecin prodrug which is converted by endogenous carboxylesterases to the active topoisomerase I poison SN-38 [Masuda 1996]. In preclinical studies, irinotecan was highly active in vitro and in vivo against a broad spectrum of human and murine tumor cell lines. Substantial antitumor activity was observed in xenografts derived from pediatric tumors, including RMS, peripheral primitive neuroectodermal tumors as well as in RMS xenografts selected in vivo for resistance to vincristine, melphalan and topotecan [Hare 1997, Houghton 1993, Komuro 1994, Thompson 1997, Vassal 1996, Vassal 1997]. This preclinical activity can be optimized by protracted

administration on a 5 days x 2 schedule, in which drug is given for five consecutive days for two weeks in a row, thus prolonging the exposure of this S-phase-specific agent [Bomgaars 2001, Houghton 1995]. A protracted schedule also seems to be less myelotoxic than other regimens evaluated [Furman 1999, Gerrits 1997].

Two distinct patterns of diarrhea have been associated with irinotecan. Early-onset diarrhea typically occurs within 4 hour of administration, and is associated with the “cholinergic syndrome” consisting of cramping, flushing, and diaphoresis [Kawato 1993]. These symptoms occur in 9–27% of children receiving single large dosages of irinotecan [Bomgaars 2006, Vassal 2003, Vassal 2007], although its incidence is < 5% in patients treated with protracted schedules [Bisogno 2006, Furman 1999, Wagner 2007]. This syndrome results from direct inhibition of acetylcholinesterase by the terminal dipiperidino moiety in irinotecan [Harel 2005]. Early-onset diarrhea is preventable or readily reversible with atropine administration [Vassal 2007], and to date has not been dose-limiting. In contrast, late-onset diarrhea usually develops during the second week of therapy, and can be dose-limiting regardless of the irinotecan schedule. In adults receiving single large dosages once every 1–3 weeks, irinotecan-associated diarrhea of any grade occurs in up to 80% of patients, with approximately 30% experiencing at least grade 3 diarrhea [Saltz 2000].

For children receiving 5 days x 2 intravenous irinotecan at the maximum tolerated dose of 20 mg/m²/day, irinotecan-associated diarrhea of any grade occurs in 73% of patients, with 10–18% having grade 3–4 diarrhea or abdominal pain [Bisogno 2006, Pappo 2007]. The mechanisms leading to late-onset diarrhea are complicated and not completely understood. It may be the result of active metabolite SN-38 present in the intestinal lumen inducing direct cytotoxic damage to the mucosa, resulting in secretory and exudative diarrhea symptoms [Saliba 1998]. Strategies to prevent diarrhea include the use of activated charcoal and/or prophylactic antibiotics during therapy with irinotecan [Furman 2006, Sergio 2008, Wagner 2008]. Cephalosporin prophylaxis is a safe and feasible way to help optimize use of protracted irinotecan in children, and can improve both dose intensity and drug exposure. Cefixime at 8 mg/kg/day (max 400 mg) is well tolerated and can be given once daily, starting up to 5 days before chemotherapy administration and continuing throughout the course of protracted irinotecan. In addition, it does not interfere with the pharmacokinetics of irinotecan [Furman 2006, Pappo 2007, Wagner 2007].

Four pediatric phase II studies were performed to determine the tumor response rate of a range of solid pediatric tumors to irinotecan as single agent. In addition to the response rate, the safety profile and pharmacokinetics of Irinotecan were assessed in three of them. Tumor response rate was the primary efficacy endpoint for these studies:

- Bisogno *et al*/reported an overall response rate to irinotecan administered on a 5 days x2 schedule (20 mg/m²/day for 5 days a week, for 2 consecutive weeks) of 23% for a total of 32 heavily pre treated patients with sarcoma: 13 with peripheral primitive neuroectodermal tumor (PNET), 3 with desmoplastic small round cell tumor (DSRCT) and 2 with other STS. Overall response rates were 38% for peripheral PNET and 16% for RMS [Bisogno 2006].
- Bomgaars *et al* reported a specific response rate of 15.8% for patients with RMS receiving irinotecan 50 mg/m² IV for 5 days repeated every 3 weeks. Stable disease was noted for 47.1% of patients and this was seen with all tumor types [Bomgaars 2007].
- Vassal *et al*/reported an overall response rate to irinotecan (at 600 mg/m² administered as a 60-minute infusion every 3 weeks) of 11.4% (2.9% complete responses, 8.5% partial responses) for a

total of 35 patients with refractory or relapsed RMS for which standard treatments have failed [Vassal 2007].

- Pappo *et al* have demonstrated that administration of Irinotecan using a low-dose protracted schedule (20 mg/m² intravenously over 60 minutes daily 5 d x 2 weeks) is highly effective when administered as window therapy in 19 pediatric patients with newly diagnosed metastatic RMS: 42% of children had a favourable response. However, the high progressive-disease rate prompted closure of this trial [Pappo 2007].

5.3. Combination of irinotecan with vincristine

After exposure to camptothecin analogues, many cell types arrest in S phase or G2-M phase. Thompson *et al* postulated that administration of topotecan followed by vincristine, that causes depolymerization of microtubules leading to mitotic arrest and death, might have a synergistic antitumor effect. They investigated the activity of this combination against a panel of childhood solid tumor xenografts representing childhood neuroblastoma, RMS or brain tumors: the therapeutic effect was greater than additive in most models of childhood solid tumors, and toxicity data suggest that this can be administered to mice with only moderate reduction in the dose levels for each agent [Thompson 1999].

Vincristine has demonstrated activity in several xenograft models of pediatric tumors [Houghton 1984, Houghton 1987] and has an established role in the treatment of childhood cancers, in particular sarcomas.

Based on these observations, Pappo *et al* added vincristine (1.5 mg/m² at weeks 0, 1, 3 and 4) to Irinotecan (daily 5 d x 2 weeks) for patients with newly diagnosed metastatic RMS. This addition increased the window response rate (70% versus 42% with Irinotecan alone) and reduced the rate of progression (8% versus 32%) [Pappo 2007].

More recently, Mascarenhas *et al* reported the results of a randomized phase II window study of two schedules of irinotecan and vincristine in RMS at first relapse/disease progression.

Patients were randomized to one of two schedules of irinotecan-vincristine : A : irinotecan 20 mg/m² intravenously (IV) daily x 5d x 2w and vincristine 1.5 mg/m² IV on day 1 of weeks 1 and 2 versus B : irinotecan 50 mg/m² IV daily x 5d on week 1 and vincristine identical to A. There were no difference in the response rates (overall response 25% versus 37%, p=0.23), no unexpected toxicities or significant differences in toxicity between the two regimens. The shorter, more convenient CPT-11/VCR regimen is now being investigated in frontline Children's Oncology Group RMS clinical trials [Mascarenhas 2010].

5.4. Temozolomide

The mechanism of action of irinotecan - mainly S phase specific obstruction of DNA replication - supports its use combined with an alkylating agent as a strategy for increasing tumor-cell kill. Imidazotetrazine compounds (TZC) are alkylating agents with antitumor and antimetastatic potential. Dacarbazine, the first TZC to be utilized in cancer patients, was used for the treatment of malignant melanoma and, in combination regimens, for the treatment of sarcomas [Antman 1993, Zucali 2008].

TMZ is a second generation imidazotetrazine prodrug that is metabolized to the active metabolite monomethyl triazenoimidazole carboxamide (MTIC) [Stevens 1987]. This agent promotes

cytotoxicity primarily via O6-methylation of guanine, leading to base-pair mismatch and eventual inhibition of DNA replication, resulting in cell cycle arrest [Catapano 1987, Newlands 1997]. It has the advantages of excellent oral bioavailability, a favorable toxicity profile, and the ability to cross the blood–brain barrier. Recently, Diez *et al*/ demonstrated the exposure equivalence of a 90-min intravenous infusion with oral administration of TMZ. Intravenous administration of TMZ was well tolerated. In clinical practice, oral TMZ is administered using a variety of doses and schedules. Based on the data from this study and the known PK characteristics of TMZ, intravenous administration would result in an equivalent exposure compared with oral administration at any given dose and schedule [Diez 2009].

Preclinical studies demonstrate an antitumor effect in murine models of pediatric solid tumors [Middlemas 2000]. TMZ has activity against adult and pediatric primary brain tumors as well as adult solid tumors with brain metastases, metastatic melanoma, and metastatic leiomyosarcoma [Anderson 2005, Nicholson 1998, Nicholson 2007, Rubie 2006, Ruggiero 2006, Verschuur 2004, Woll 1999]. However, data on the use of TMZ as a single agent in other pediatric malignancies are limited. De Sio *et al*/investigated the use of TMZ as single agent in 52 relapsed or resistant pediatric tumors. They reported activity of TMZ in relapsed or resistant neuroblastoma patients and in a subset of patients with CNS tumors. TMZ did not induce any major response in other tumor types [De Sio 2006].

5.5. Combination of irinotecan with temozolomide

Although it is unclear exactly how the cytotoxicity of irinotecan is potentiated by TMZ, it may be related to TMZ -induced methylation of DNA causing localization and enhancement of topoisomerase I cleavage complexes allowing irinotecan to more effectively stabilize the DNA-enzyme complex and cause cytotoxicity after collision with advancing replication fork.

In addition to the single-agent activity and non-overlapping toxicity profiles (diarrhea versus myelosuppression), this combination is attractive because of significant therapeutic synergy demonstrated by Houghton *et al*/ [Houghton 2000] in preclinical experiments. They showed that the combination of non curative doses of each drug resulted in complete responses in xenograft models of neuroblastoma, rhabdomyosarcoma RMS, and glioblastoma multiforme. This occurred in tumors that were MGMT sufficient and mismatch repair (MMR) deficient, suggesting that the interaction between these agents may in part be independent of TMZ induced O6-methylation of guanine. This therapeutic synergy is greatest when TMZ is given before irinotecan, suggesting that TMZ potentiates the cytotoxic effects of irinotecan [Patel 2000].

This rationale has led to adult phase I and II trials of this combination in brain tumors [Gruber 2004] and solid tumors [Jones 2003].

A pediatric phase I trial has identified the MTD for TMZ to be 100mg/m²/day given x5 days combined with irinotecan 10 mg/m²/d given 5 days x 2 given in 28-day cycles. Despite these relatively low doses, clinically relevant SN-38 and MTIC exposures were achieved at the MTD and objective imaging responses were seen in over one-third of evaluable patients particularly for patients with neuroblastoma and Ewing sarcoma [Wagner 2004]. A phase II trial with this schedule is currently ongoing in children with relapsed medulloblastoma [Grill *et al*, ASCO 2009].

Kushner *et al* chose a 5-day plan of irinotecan 50 mg/m² (1-hour infusion) and TMZ 150 mg/m² (oral) every 3 to 4 weeks because of its convenience for patients. These courses of irinotecan and TMZ in a large series of heavily treated neuroblastoma patients had manageable adverse effects and no unexpected toxicities. The regimen was compatible with normal age-appropriate activities. Ease and rapidity of administration, plus little emetogenic effect, allowed outpatient treatment. When they occurred, gastrointestinal symptoms were generally self-limited, of short duration, or responsive to standard medications [Kushner 2006].

While TMZ has little clinical activity as a single agent against sarcomas, it may serve as a response modifier to potentiate the antitumor activity of irinotecan.

In a retrospective review, Wagner *et al* reported their clinical experience with TMZ and protracted irinotecan in patients with advanced Ewing sarcomas [Wagner 2007]. These patients received different doses of irinotecan and different lengths of treatment courses. The authors observed 1 complete, 3 partial and 3 minor responses in 14 evaluable patients with a median duration of 30 weeks. Another recent retrospective analysis builds on these observations, reporting an overall objective best response of 63% with the use of protracted irinotecan (20 mg/m²/day x5days x2weeks) in combination with TMZ (100mg/m²/dayx5days) for recurrent/ progressive Ewing sarcomas. It is notable that 5 (26%) of 19 evaluable patients achieved a complete response [Casey 2009].

5.6. Combination of irinotecan with vincristine and temozolomide

In a recent phase I trial, Wagner *et al* determined the dose limiting toxicities (DLTs) and maximum tolerated dose (MTD) of orally administered irinotecan given on two different schedules together with TMZ and vincristine in children with refractory solid tumors, using cefixime to reduce irinotecan-associated diarrhea. The schedule A associated oral irinotecan daily for 5 days for 2 weeks (5 days x2), with vincristine 1.5 mg/m² on days 1 and 8 and TMZ 100 mg/m² on days 1-5. The schedule B associated oral irinotecan daily for 5 days for 1 week (5 days x1) with vincristine 1.5 mg/m² on day 1 and TMZ 100-150 mg/m² on days 1-5. Courses were repeated every 3 weeks. First-course and cumulative toxicity appeared worse with schedule A. The 5 days x1 schedule was well tolerated, with SN-38 exposures similar to those achieved with intravenous IRN at the dose of irinotecan 90 mg/m²/day. Activity on this and prior studies suggests a potential role for this association in sarcoma patients [Wagner 2009].

The current open-label, multicenter, randomized phase II study will evaluate the efficacy and tolerability of combination of TMZ with vincristine and irinotecan for 80 patients with refractory or recurrent RMS, and for 40 additional patients with recurrent RMS only (upon IDMC decision).

Given the results of Mascarenhas *et al* and of Wagner *et al* and because of its convenience for patients, we chose a 5-day plan of administration for irinotecan.

Depending on the results of this trial, the VIT combination could become a backbone chemotherapy in relapsed or refractory RMS, using three drugs of which two are not used in front line treatment. Further trials could be designed incorporating TMZ with new compounds such as targeted or antiangiogenic compounds, PARP inhibitors etc.

6. STUDY OBJECTIVES

6.1. Primary objectives

- To assess the rate of confirmed objective tumor response in patients with recurrent or refractory rhabdomyosarcoma in each treatment arm

6.2. Secondary objectives

- To describe the best overall response over the treatment duration, determine the duration of tumor response, progression-free survival (PFS), time to treatment failure and overall survival (OS) in each treatment arm.
- To assess safety and tolerability for each treatment arm.

6.3. Ancillary objective

- To estimate the relative treatment effect of VIT compared to VI in terms of objective response rate (ORR), PFS and OS (after amendment 5.0 July 2018).

7. STUDY DESIGN

7.1. Type of study

This is an international open-label, randomized, multicenter phase II study of VIT and VI for the treatment of 80 patients with recurrent or refractory RMS, and 40 additional patient with recurrent RMS only (upon IDMC decision). The study will evaluate the safety and efficacy of these combinations in patients with recurrent or refractory RMS.

The dose of vincristine will be 1.5 mg/m² or 0.05 mg/kg for patient ≤ 10 kg (maximum 2 mg) and will be administered by direct intravenous infusion on day 1 and 8 of each course, before irinotecan.

The dose of irinotecan will be 50 mg/m²/d. Irinotecan will be given intravenously infusion over 1 hour on days 1-5 of each course, one hour following the administration of TMZ.

In the absence of any contraindication (ie known allergies), treatment with oral cefixime 8 mg/kg once daily (maximum daily dose 400 mg) is recommended and will be started 2 days before chemotherapy until day 7 (see Appendix 11 for cefixime management in The Netherlands).

TMZ will be given according to the randomization. The starting dose of TMZ will be 125 mg/m²/d. The dose of TMZ will be escalated to 150 mg/m²/day at cycle 2 for patients who do not experience ≥ grade 3 toxicity of any kind. TMZ will be given orally, on an empty stomach, on days 1 through 5 of each course. The capsules must be swallowed whole with a glass of water. For young children and patients who have difficulty swallowing capsules, the full daily dose of TMZ capsules should be placed in 10-30 ml fruit juice or compote and administered after the capsules have been allowed to soften for 15-20 minutes.

Dose reductions and/or administration delays will be performed using specific predefined rules to accommodate individual patient tolerance of treatment and to maintain optimal dose intensity (section 8.3.5.).

7.2. End of study

If the study is not terminated for one of the reasons given in section 7.3., the main analysis will be performed when the end of treatment imaging on the last patient has been undertaken. The Last Visit of the Last Subject (LVLS) is defined as last VI/VIT administration + 6 months to have relevant data in terms of response after 2 cycles.

The final analysis of survival outcomes is planned 5 years after recruitment of the last patient.

7.3. Study discontinuation

Although the Investigator-Sponsor has every intention of completing the study, the Investigator-Sponsor reserves the right to discontinue the study at any time for clinical or administrative reasons.

Reasons for terminating the study may include:

- Unexpected incidence of known AEs.
- Medical or ethical reasons affecting the continued performance of the study.
- Difficulties in the recruitment of patients.

7.4. Inclusion criteria

Patients must satisfy all the following entry criteria before they are allowed to participate in the study.

TUMOR CHARACTERISTICS:

- Histologically or cytologically confirmed diagnosis of rhabdomyosarcoma (new biopsy recommended)
- Any Relapsed / progressive disease (in patients who have already presented a response to chemotherapy)

OR

- Refractory disease (defined as progression after receiving chemotherapy without prior response)
- Patients must have measurable disease defined as lesions that can be measured in 3 dimensions by medical imaging techniques such as CT or MRI. Ascites, pleural fluid, bone marrow disease alone and lesions seen on Tc scintigraphy or PET scan only are not considered measurable.

PATIENT CHARACTERISTICS:

- Age > 6 months and ≤ 50 years
- Karnofsky performance status (PS) 70-100% (for patients > 12 years of age)
OR Lansky Play Score 70-100 % (for patients ≤ 12 years of age)
- Life expectancy ≥ 12 weeks
- Adequate bone marrow function :
 - Absolute neutrophil count ≥ 1000/mm³
 - Platelet count ≥ 100,000/mm³ (transfusion independent)
 - Hemoglobin ≥ 8.5 g/dL (transfusion allowed)

- In case of bone marrow disease:
 - Absolute neutrophil count $\geq 500/\text{mm}^3$
 - Platelet count $\geq 75,000/\text{mm}^3$
- Adequate renal function
 - Serum creatinine $\leq 1.5 \times \text{ULN}$ for age
 - If serum creatinine $> 1.5 \text{ ULN}$, creatinine clearance (or radioisotope GFR) must be $\geq 70 \text{ ml/min/1.73 m}^2$
- Adequate hepatic function :
 - Total bilirubin ≤ 1.5 times upper limit of normal (ULN) for age, except if the patient is known to have Gilbert's syndrome
 - ALT and AST $\leq 2.5 \times \text{ULN}$ for age
- Negative pregnancy test in females with childbearing potential
- Fertile patients must use effective contraception
- No active $>$ grade 2 diarrhea or uncontrolled infection
- No other malignancy, including secondary malignancy
- Patient affiliated with a health insurance system. Applicable for French patients only
- Written informed consent of patient and/or parents/ guardians

PRIOR OR CONCURRENT THERAPY:

- More than 3 weeks since prior radiation therapy to the site of any progressive lesion that will be identified as a target lesion to measure tumor response
- At least 3 weeks since prior myelosuppressive therapy (6 weeks for nitrosourea, 2 weeks for vincristine, vinorelbine, vinblastine and low-dose cyclophosphamide)
- No concurrent enzyme-inducing anticonvulsants (EIA), including phenytoin, phenobarbital, or carbamazepine
- No concurrent administration of any of the following : rifampicin, voriconazole, itraconazole, ketoconazole, aprepitant
- No prior irinotecan or temozolomide administration
- Prior administration of vincristine is allowed
- Concurrent palliative radiation therapy to sites allowed except for the main measurable target lesion
- Prior allo- or autologous SCT allowed

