Revised study design after amendment 4.0, in December 2015

IDMC reviewed the data analysis of the first 80 patients.

At that date, 80 patients (68 in the relapse status) had been enrolled with an annual accrual rate of 28 patients, which is higher than expected.

Based on the analysis, the IDMC considered that preliminary results indicate that more precision is needed, not only for the primary endpoint, but also for the secondary endpoints which will be used in planning the next phase III trial. They recommended that, in order to obtain a sufficient power to differentiate both arms and not to stop the European dynamic, the inclusion of a total of 120 patients (108 patients in the relapse status) in the VIT trial, should allow sufficient accuracy for choosing the standard arm: VI or VIT. The accrual of 40 extra patients should prolong the VIT trial one year.

The increase in the sample size is justified by the change in the statistical hypotheses since the IDMC recommended continuing the inclusion of only patients in relapse, refractory patients being no longer eligible for inclusion. Also, since the next trial will not be ready for another year, the extra patients in this trial should allow sufficient accuracy for choosing the standard arm in the next trial. The new design parameters are the following ($p_0=0.35$, $p_1=0.55$, $a=0.10$ and $b=0.10$) which lead to 47 evaluable patients. With 15% of lost follow-up (ineligible and non evaluable), 54 patients per arm should be included, for a **total of 108 randomized relapse patients**. Since 68 patients in relapse are already included, a total of **40 additional patients** in the relapse status should be included. With the new design parameters, if at least 22 patients among the 47 in the VIT arm show a treatment success, the treatment can be considered as sufficiently active. If 21 or less among 47 patients in the VIT arm have a treatment success, the treatment is considered insufficiently active.

Randomization 1:1 will be stratified for recurrent vs. refractory status and country for the first 80 patients. For the 40 additional patients in the relapse status, stratification by minimization will be performed for prior radiotherapy (yes vs no), country and recurrence (metastatic vs locoregional) according to the importance of these factors on the PFS curve.

12.2.

Statistical analyses

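### The inclusion list in section 7.4 still admits refractory disease without limit, contradicting the relapse-only revised design in sections 5.6, 7.1 and 12.1

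*Protocol*

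**What the plan says.** Section 7.4 opens with a rule for every entrant: "Patients must satisfy all the following entry criteria before they are allowed to participate in the study". Under tumour characteristics it offers two qualifying states joined by OR. One is relapsed or progressive disease after an earlier response to chemotherapy. The other is "Refractory disease (defined as progression after receiving chemotherapy without prior response". Neither is tied to a period or to a block of patients. The exclusion list in section 7.5 does not mention refractory disease.

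Section 12.1, under the design revised at amendment 4.0, explains that the hypotheses changed "since the IDMC recommended continuing the inclusion of only patients in relapse, refractory patients being no longer eligible for inclusion". It sets new response rates (0.35 and 0.55, both error rates 0.10) "which lead to 47 evaluable patients", a target of 108 randomised relapse patients, and 40 further patients in relapse. Section 7.1 describes "80 patients with recurrent or refractory RMS, and 40 additional patient with recurrent RMS only (upon IDMC decision", and section 5.6 says the same.

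Two other places depend on the entry criteria. Section 7.7 has all inclusion and exclusion criteria checked at registration. The statistical analyses part of section 12 defines eligible patients as those without a major violation of the inclusion and exclusion criteria, and builds the per-protocol population on that definition.

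**The concern.** These are two current parts of the same protocol version, so this is not a difference between the text in force and the amendment log. When amendment 4.0 narrowed the population, the design description and the sample-size section were updated, but the list used to admit patients was not.

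A refractory patient presenting after amendment 4.0 satisfies section 7.4 and is excluded by section 12.1. The protocol does not say whether enrolling that patient is a violation, whether the patient belongs in the per-protocol population, or whether the patient counts toward the 47.

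The answer matters because the revised design has no room for such patients. Section 12.1 justifies the move from 0.20 and 0.40 to 0.35 and 0.55 by the restriction to relapse. The 108, the 40 and the 22-of-47 rule follow from those rates. For the last 40 patients the stratification by recurrent versus refractory status is replaced by minimisation on prior radiotherapy, country and metastatic versus locoregional recurrence. That is coherent only if no refractory patient can enter.

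**Working it through.** **1. The provisions side by side**

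| Place | Who may enter after amendment 4.0 |
|---|---|
| 5.6 and 7.1 | The 40 additional patients: recurrent disease only |
| 7.4 | Relapsed/progressive OR refractory, no limit |
| 7.5 | No exclusion of refractory disease |
| 12.1, revised design | Relapse only; refractory no longer eligible |
| 12.1, randomisation | No refractory factor for the last 40 |

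Section 7.4 stands apart from the rest.

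**2. The plan's own figures reproduce**

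- An exact search for the Simon optimal two-stage design at p0 = 0.35, p1 = 0.55, alpha = beta = 0.10 gives n = 47, as stated.
- The stated rule, at least 22 of 47, taken as a single stage: type I error 0.063, power 0.899.
- Allowance for 15% loss: 47 × 1.15 = 54.05, the stated 54 per arm.
- Total: 2 × 54 = 108. Additional patients: 108 − 68 = 40.

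Bringing section 7.4 into line leaves all of these unchanged.

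**3. Illustration A: refractory patients take places and are left out of the test**

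Inputs from section 12.1: 80 enrolled, 68 in relapse, 40 extra places, 15% loss. Assumption: refractory entry continues at the earlier rate, as if the restriction stated elsewhere had no effect.

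- Earlier share not in relapse: (80 − 68) / 80 = 12 / 80 = 15%.
- Places lost: 40 × 0.15 = 6.
- Relapsed patients: 68 + 34 = 102.
- Evaluable relapsed per arm with no refractory entry: 108 × 0.85 / 2 = 45.9.
- With 6 refractory entries: 102 × 0.85 / 2 = 43.35, or 43.4.
- Effect of section 7.4: 45.9 − 43.35 = 2.55 per arm.

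The remaining 47 − 45.9 = 1.1 per arm exists with no refractory entry at all. It arises because the 15% was applied as 47 × 1.15 = 54 and not as 47 / 0.85 = 55.3, rounded up to 56.

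**4. Illustration B: the same patients are instead counted in the test**

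This is an alternative to A. The same patients cannot be both left out and counted. The documents give no refractory response rate, so 10% to 35% is assumed, with 55% for relapsed patients. With refractory share s and refractory response rate q, the mixed rate is (1 − s) × 0.55 + s × q, put into the exact binomial for at least 22 of 47.

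| Refractory share of the 47 | Power, q = 10% | Power, q = 35% |
|---|---|---|
| 0 | 0.90 | 0.90 |
| 5% | 0.83 | 0.87 |
| 10% | 0.74 | 0.84 |
| 15% | 0.63 | 0.80 |

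Six refractory patients split evenly would be 3 of 54 per arm, or 5.6%, so the 5% row is the nearest to illustration A.

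**The case against.** The strongest reply is that the protocol states the restriction several times, in sections 5.6, 7.1 and 12.1, and that section 7.4 describes the whole 120-patient trial. Twelve of the first 80 were not in relapse, so the refractory criterion could not simply be deleted. On that reading only a cross-reference is missing. This explains how the text arose and makes heavy refractory entry unlikely. It does not remove the conflict, because section 7.4 addresses every entrant and does not say which criterion applied to which patients.

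A reader might infer that a refractory patient enrolled late simply counts as eligible. The documents do not support that: section 12.1 says the opposite, and section 7.7 does not make section 7.4 the sole authority. The status is contradictory, no more. The per-protocol population also serves only secondary analyses, while the main analysis is by intention to treat.

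A reader might also set 43.4 evaluable per arm against 47 and put the whole gap down to section 7.4. Part of it is there without any refractory patient. Six in 40 is itself a worst case, and nothing in the protocol shows that any refractory patient entered after amendment 4.0.

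The new minimisation factors suggest that randomisation was set up for relapse only. That supports reading section 12.1 as the intended rule, and so supports aligning section 7.4 with it.

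Finally, section 12.1 expected the extra accrual to take about a year from December 2015, and the current version dates from June 2019. Enrolment may be over, in which case the correction mainly settles how any late refractory inclusion is classified and analysed.

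**Conclusion.** The concern holds as an internal contradiction. Section 7.4 admits refractory disease without limit, while sections 5.6, 7.1 and 12.1 confine the 40 additional patients to relapse, and the revised hypotheses, decision rule, total and minimisation all depend on that confinement. This rests on the text alone and needs no assumption.

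The numerical effect is illustrative and modest: about 2.5 evaluable relapsed patients per arm if refractory entry continued at 15% and those patients were left out of the test. If they were counted instead, power would be roughly 0.83 to 0.87 against 0.90 at a 5% share, under assumed refractory response rates. The two effects are alternatives and must not be added. The correction should be made because it is specific and nearly free, and because the entry rule is wrong as written for the last 40 patients.

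**What to change.** Reconcile section 7.4 with section 12.1. State that the refractory criterion applied to the first 80 patients only, and that the 40 additional patients must have relapsed or progressive disease after a prior response to chemotherapy. In the statistical analyses part of section 12, add that any refractory patient included among the 40 is recorded as an eligibility violation and is not counted in the relapse-only 47-patient test.

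The cost is one sentence in section 7.4 and one in section 12. No new data are needed, and 47, 54, 108, 40 and the 22-of-47 rule stay as they are.
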